6.2.1.1 Permitted concomitant therapy requiring caution and/or action

The patient should be on an optimal medical regimen of background HF medications. Use of an aldosterone antagonist should be considered in patients eligible for this study. Every effort should be made to keep the dose level of disease-modifying HF medications stable throughout the entire study. However, if the investigator believes a disease-modifying medication is causing an AE or patient's condition needs a change in any of disease-modifying HF medications, it is allowed at the discretion of the investigator. Diuretics may be used and may be adjusted throughout the length of the study at the discretion of investigator.

If patients experience any AEs that may be related to the study drug, other HF medications, or other cardiovascular medications, the investigator should adjust non-disease-modifying medications (e.g. calcium channel blocker, nitrates, α -blockers, and diuretics) first in attempt to alleviate the AEs.

Potassium-sparing diuretics (e.g., spironolactone, triamterene, amiloride), potassium supplements, aldosterone antagonists, and any other medications known to raise potassium levels should be used with caution. The investigator should assess patient's potassium levels, especially in those who are receiving these medications.

Phosphodiesterase-5 inhibitors should be used with caution while the patient is receiving study medications due to the increased possibility of occurrence of hypotension.

Page 28 of 63

In case the patient requires the concomitant administration of neseritide and/or intravenous nitrates with the study medications, the investigator should consider starting them at a lower dose or a slower infusion rate while monitoring the patient's blood pressure carefully.

Nonsteroidal Anti-Inflammatory Drugs

In patients who are elderly, volume-depleted, or with compromised renal function, concomitant use of nonsteroidal anti-inflammatory drugs, including cyclooxygenase-2 (COX-2) inhibitors, with sacubitril/valsartan may result in worsening of renal function, including possible acute renal failure.

Lithium

Increases in serum lithium concentrations and lithium toxicity have been reported during concomitant administration of lithium with angiotensin II receptor antagonists and ARBs. There is no data on this interaction as for now. Base on related data, serum lithium concentration should be monitored when concomitant sacubitril/valsartan with lithium supplement.

6.2.2 Prohibited medication

Followed by ARNI instructive document. Concomitant use of ARNI with an ACEI/ARB is contraindicated because of the increased risk of angioedema.

Bile acid sequestrants (cholestyramine and colestipol) are also prohibited to avoid disturbing effect on the drug absorption of study medication.

6.2.3 Rescue medication

There is no rescue medication, however in the event of hyperkalemia, investigator should review the medical regimen (including dietary supplements and over-the-counter medications) for agents known to cause hyperkalemia. Any patient who experiences a potassium level > 6.0 mmol/L confirmed by repeated same blood sample testing may be discontinued from the study treatment.

If symptomatic hypotension occurs, correct any treatable cause. If hypotension persists, any anti-hypertensive drug and non-disease-modifying drugs, such as diuretics, calcium channel blockers, nitrates, and α -blockers, should be down-titrated or stopped. If hypotension persists, the study drug should be temporarily withdrawn, the re-initiation of ARNI will be at Investigator discretion. ARNI is unlikely to be removed by hemodialysis because of high protein binding.

If ICD electrical storm occurs, correct the underlying arrhythmia. Differential diagnosis to the arrhythmia should be determined, with patient hospitalized and observed by an electrophysiologist. Drugs such as amiodarone and anti-arrhythmic agents can be used.

6.3 Patient numbering, treatment assignment, randomization

6.3.1 Patient numbering

Each patient is identified in the study by a Patient Number (Patient No. eight-digit code), that is assigned when the patient is first enrolled for screening and is retained as the primary identifier for the patient throughout his/her entire participation in the trial. The Patient No. consists of the Center Number (Center No. four-digit code) (as assigned by Novartis to the investigative site) with a sequential patient number suffixed to it, so that each patient is numbered uniquely across the entire database.

6.3.2 Treatment assignment, randomization

This is a single-arm study, no treatment assignment will be involved in this study. No randomization will be performed in this study.

6.4 Treatment blinding

Treatment will be open to patients, investigator staff, persons performing the assessments, and the clinical trial team (CTT).

6.5 Dose escalation and dose modification

Investigational or other study treatment dose adjustments and/or interruptions are under investigator's discretion and according to product labels. Up-titration of patient's drug should be according to the target dose or to the patient's maximum tolerance level.

6.5.1 Dose escalation guidelines

The dosage of ACEI/ARB and ARNI are under Investigator's discretion according to the recommended dosage (Yancy et al 2017) (Table 6-2). The recommended starting dose of ARNI for different population is presented in (Table 6-3). If the patient is well tolerated, the dose of study drug should be up-titrated to next dose level until to target dose. Down-titration of the study drug at any time based on the judgment of the Investigator will be allowed with the consideration for patient safety and tolerability.

Table 6-2 Recommended dosage

Compound	Initiation dosage	Target dosage	
ARNI (Sacubitril/Valsartan)	50 – 100 mg bid	200 mg bid	
ACEI			
Enalapril	2.50 mg bid	10 mg bid	
Captopril	6.25 mg tid	50 mg tid	
Perindopril	2.00 mg qd	8 mg qd	
Ramipril	1.25 mg qd	10 mg qd	
Benazepril	2.5 mg qd	20 mg qd	

ARB

Compound	Initiation dosage	Target dosage
Candesartan	4 mg qd	32 mg qd
Valsartan	40 mg bid	160 mg bid
Losartan	25 – 50 mg qd	150 mg qd

Table 6-3 Recommended starting dose of ARNI

Population	Initial dose
Moderate or high-dose ACEI (equivalent of enalapril ≥10 mg bid)	100 mg bid
Moderate or high-dose ARB (equivalent of valsartan ≥80 mg bid)	100 mg bid
Low dose ACEI (equivalent of enalapril <10 mg bid)	50 mg bid
Low dose ARB (equivalent of valsartan <80 mg bid)	50 mg bid
Severe renal impairment (eGFR <30 mL/min/1.73 m ²)	50 mg bid
Moderate hepatic impairment (Child-Pugh Class B)	50 mg bid
Elderly (age ≥75 years)	50 mg bid

6.5.2 Definitions of dose limiting toxicities

A dose limiting toxicity (DLT) is defined as an adverse event or abnormal laboratory value assessed as unrelated to disease, disease progression, inter-current illness, or concomitant medications that occurs when taking study drugs. Dosage of study drugs is according to product label. Patients who meet any of the DLTs defined in the product label will be withdrawn from this study.

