Other treatment	Treatment that may be needed/allowed during the conduct of the study (i.e. concomitant or rescue therapy).	
Part	A sub-division of a study used to evaluate specific objectives or contain different populations. For example, one study could contain a single dose part and a multiple dose part, or a part in participants with established disease and in those with newly-diagnosed disease.	
Patient	An individual with the condition of interest for the study.	
Patient number	A unique number assigned to each patient upon signing the informed consent. This number is the definitive, unique identifier for the patient and should be used to identify the patient throughout the study for all data collected, sample labels, etc.	
Period	The subdivisions of the trial design (e.g. Screening, Treatment, Follow-up) which are described in the Protocol. Periods define the study phases and will be used in clinical trial database setup and eventually in analysis.	

Personal data	Patient information collected by the Investigator that is coded and transferred to Novartis for the purpose of the clinical trial. This data includes patient identifier information, study information and biological samples.	
Premature participant withdrawal Point/time when the patient exits from the study prior to the planned completion of all study drug administration and/or assessments; at this study drug administration is discontinued and no further assessments applanned.		
Randomization number	A unique identifier assigned to each randomized patient.	
Run-in Failure	A patient who is screened but not randomized/treated after the run-in period (where run-in period requires adjustment to patient's intervention or other treatment).	
Screen Failure	A patient who did not meet one or more criteria that were required for participation in the study.	
Source Source data refers to the initial record, document, or primary location where data comes. The data source can be a database, a dataset, a spreadsheet or even hard-coded data, such as paper or eSource.		
Start of the clinical trial	The start of the clinical trial is defined as the signature of the informed consby the first patient.	
Study treatment	Any drug or combination of drugs or intervention administered to the patients as part of the required study procedures; includes investigational drug(s) or control(s).	

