2.1 Primary estimands

The primary clinical question of interest is: What is the effect of the ARNI versus ACEI/ARB on change on VA and ICD or CRT-D shocks and ATP in patients with implanted ICD or CRT-D?

The justification for the primary estimand is that it will capture both the effect of the study drug and the effect of additional medications, mirroring the conditions in clinical practice. Further details can be found in Section 12.

The primary estimand is described by the following attributes:

- 1. Population: patients defined through appropriate inclusion/exclusion criteria to reflect the targeted patient population for approval. Further details about the population are provided in Section 5.
- 2. Variable: VA, ICD and ATP events over 6 months of ACEI/ARB and 6 months of ARNI treatment.
- 3. Treatment of interest: ACEI/ARB for 6 months and ARNI for 6 months. Further details about the investigational treatment and control treatment are provided in Section 6.

Handling of remaining intercurrent events:

- 1. Treatment discontinuations for any reason: ignore (treatment policy strategy).
- 2. Unforeseen change in the dose of allowed concomitant medications: ignore (treatment policy strategy).
- 3. Unforeseen change in the dose of the investigational treatment or the control treatment due to adverse event or other reason: ignore (treatment policy strategy).

The summary measure: Proportion of patients with VA, ICD and ATP events over 6 months of ACEI/ARB and 6 months of ARNI treatment

[figure not shown]

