6.2 Other treatments

6.2.1 Concomitant therapy

All medications, procedures, and significant non-drug therapies (including physical therapy and blood transfusions) administered after the patient was enrolled into the study must be recorded on the appropriate electronic Case Report Forms (eCRF).

Each concomitant drug must be individually assessed against all exclusion criteria and prohibited medication. If in doubt, the Investigator should contact the Novartis medical monitor before allowing a new medication to be started. If the patient is already enrolled, contact Novartis to determine if the patient should continue participation in the study.

The concomitant use of other ACEIs or ARBs is strictly prohibited while the patient is receiving ARNI. Study medication should be stopped the day prior to addition of other ACEIs or ARBs.

Drugs for arrhythmia include antiarrhythmic drugs (amiodarone), beta-2 blockers (metoprolol sustained release tablets), and digitalis drugs (digoxin). Except for titration dose adjustment of beta-2 beta blockers, no special dose adjustment for other drugs. Amiodarone dosage must be consistent for patient treatment during this study, if radiofrequency ablation is necessary, the patient should withdraw from the study.

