Information about common side effects already known about the investigational drug can be found in the label. This information will be included in the patient informed consent and should be discussed with the patient during the study as needed. Any new information regarding the safety profile of the investigational drug that is identified between label updates will be communicated as appropriate, for example, via an investigator notification (IN) or an aggregate safety finding. New information might require an update to the informed consent and then must be discussed with the patient. In the event of recollection of informed consent is needed, the Investigator may conduct the informed consent discussion remotely (e.g., telephone or video conference). Guidance issued by local regulatory bodies, and ECs/IRBs on this aspect prevail and must be implemented and appropriately documented (e.g., the presence of an impartial witness, sign/dating separate ICFs by trial participant and person obtaining informed consent, etc.).

Women of childbearing potential must be informed that taking the study treatment may involve risks to the fetus if pregnancy were to occur during the study and agree that in order to participate in the study they must adhere to the contraception requirements.

Male patients must be informed that if a female partner becomes pregnant while he is enrolled in the study, contact with the female partner will be attempted to request her consent to collect pregnancy outcome information.

8 Visit schedule and assessments

The Assessment Schedule (Table 8-1) lists all of the assessments when they are performed. All data obtained from these assessments must be supported in the patient's source documentation.

Patients should be seen for all visits/assessments as outlined in the assessment schedule (Table 8-1) or as close to the designated day/time as possible. Missed or rescheduled visits should not lead to automatic discontinuation.

Patients who discontinue from the study treatment are to complete the end of treatment visit as soon as possible, and attend the follow-up visits as indicated in Table 8-1.

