Patients who discontinue from study should be scheduled for a final evaluation visit if they agree, as soon as possible, at which time all of the assessments listed for the final visit will be performed. At this final visit, all dispensed investigational product should be reconciled, and the adverse events and concomitant medications not previously reported must be recorded on

the eCRF. All treated patients should have a safety follow-up call conducted 30 days after last administration of study treatment.

Table 8-1 Assessment schedule

Period	Screening	A	CEI/ARB treatme	ent	ARNI treatment		
Visit name	1	2	3	4	5	6	7
Week/Month	0	1m (± 1w)	3m (± 2w)	6m (± 2w)	7m (± 1w)	9m (± 2w)	12m (± 2w)
Obtain informed consent	Х						
Inclusion/exclusion criteria	Х						
Demography	Х						
Date of birth							
Age							
Gender							
Race							
Height (cm)							
Weight (kg)							
BMI (kg/m²)							
Source of patient referral							
Patient HF History	Х						
Relevant medical history/current medical history	X						
Prior HF medications	Х						
Prior/Concomitant Medications	X	X	X	X	X	X	X
Implanted device	X						
Date of implantation							
ICD or CRT-D							
Primary prevention or secondary prevention							
Device data	Х	X	X	X		X	X
VA events (SVT, NSVT, PVC)							
ICD or CRT-D shocks (appropriate shocks and inappropriate shocks)							
Anti-tachycardia pacing (%)							

Physical examinations	Х	Х	Х	Х	Х	Х	Х
Electrocardiogram (ECG) data	Х		Х	Х		Х	Х
Holter monitor	Х			Х			Х
Echocardiographic data	Х			X			Х
LVEF (%)							
LVEDD (mm)							
Vital signs	X	Х	X	X	Х	X	X
Systolic blood pressure (mmHg)							
Diastolic blood pressure (mmHg)							
Heart rate average (bpm)							
Hematology test	X			X			X
Routine blood test							
Chemistry test							
Serum potassium (mEq/L)							
NT-proBNP (pg/mL)							
eGFR (mL/min/1.73m ²)							
blood pregnancy test							
Urinary pregnancy test	X			X			X
NYHA class (I-IV)	Х	Х	X	X	Х	Х	Х
Adverse Events	Х	Х	X	X	Х	Х	Х
Hospital admission data	Х	Х	X	X	Х	Х	Х
Study treatment administration	Х	Х	X	X	Х	X	Х
Study treatment dispense (ARNI)				Х	Х	Х	
Diary card collection		Х	Х	Х	Х	Х	Х
Study patient compliance assessment		Х	Х	Х	Х	Х	Х
Study completion status							Х

Abbreviations: ACEI = Angiotensin-converting enzyme inhibitor; ; ARB = Angiotensin receptor blockers; ARNI = Angiotensin receptor neprilysin inhibitor; ; CRT-D = cardiac resynchronization therapy-defibrillator;

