9.1 Discontinuation and completion

9.1.1 Study treatment discontinuation and study discontinuation

Discontinuation of study treatment for a patient occurs when study treatment is stopped earlier than the protocol planned duration, and can be initiated by either the patient or the investigator.

The investigator must discontinue study treatment for a given patient if, he/she believes that continuation would negatively impact the patient's well-being.

Discontinuation from study treatment is required under the following circumstances:

- 1. Patient/guardian decision
- 2. Pregnancy
- 3. Use of prohibited treatment as per recommendations in the prohibited treatment section
- 4. ACEI/ARBs daily dosage below guided dosage last for 1 month
- 5. Any situation in which study participation might result in a safety risk to the patient
- 6. Withdrawal of informed consent

Study treatment may be discontinued at the investigator's discretion if any of the following occurs:

- 1. Any severe, or suspected AE, that may jeopardize patient well-being, if the study drug is continued
- 2. Suspected occurrence of angioedema
- 3. Serum potassium >6.0 mmol/L at follow Visit
- 4. Any laboratory abnormalities that in the judgment of the investigator, taking into consideration the patient's overall status, prevents the patient from continuing participation in the study

If discontinuation of study treatment occurs, the Investigator should make a reasonable effort to understand the primary reason for the patient's premature discontinuation of study treatment and record this information.

Patients who discontinue study treatment or who decide they do not wish to participate in the study further should NOT be considered withdrawn from the study UNLESS they withdraw their consent (see withdraw of informed consent section). Where possible, they should return for the assessments indicated in the assessment schedule. If they fail to return for these assessments for unknown reasons, every effort (e.g. telephone, email, letter) should be made to contact the patient/pre-designated contact as specified in the lost to follow-up section. This contact should preferably be done according to the study visit schedule. Patients are to be discontinued from the study treatment if patient has not received the study treatment for > 14 days.

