If the patient cannot or is unwilling to attend any visit(s), the site staff should maintain regular telephone contact with the patient, or with a person pre-designated by the patient. This telephone contact should preferably be done according to the study visit schedule.

After discontinuation from study treatment, at a minimum, in abbreviated visits, the following data should be collected at clinic visits or via telephone/email contact:

- New/concomitant treatments
- Adverse events/SAE

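### Protocol 6.5.2 and SAP 3.3.2 withdraw patients with a dose limiting toxicity from the study, contradicting 9.1.1 and losing device data that the treatment-policy estimand needs

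*Protocol*

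**What the plan says.** Protocol 6.5.2 (Definitions of dose limiting toxicities) rules: "Patients who meet any of the DLTs defined in the product label will be withdrawn from this study". SAP 3.3.2 repeats the rule in the same words.

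Protocol 9.1.1 separates stopping treatment from leaving the study. Patients who stop study treatment "should NOT be considered withdrawn from the study UNLESS they withdraw their consent", and where possible they return for the scheduled assessments. Severe adverse events, suspected angioedema and potassium above 6.0 mmol/L are listed there only as grounds on which the investigator may stop study treatment.

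In Protocol 2.1 the first intercurrent event reads: "Treatment discontinuations for any reason: ignore (treatment policy strategy".

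Status decides what is collected. Under Protocol 8 (Visit schedule and assessments), patients who stop treatment are to "attend the follow-up visits as indicated in Table 8-1". The same section treats those who leave the study differently: "Patients who discontinue from study should be scheduled for a final evaluation visit if they agree". The glossary entry on premature withdrawal says "study drug administration is discontinued and no further assessments", with the last words garbled in the extracted text but evidently meaning that none are planned.

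For patients seen only in abbreviated form after stopping treatment, 9.1.1 sets a floor: "at a minimum, in abbreviated visits, the following data should be collected at clinic visits or via telephone/email contact". The list that follows contains new or concomitant treatments and adverse events. Device data are not on it.

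**The concern.** A DLT is defined in 6.5.2 as an adverse event or abnormal laboratory value occurring on study drug. The same patient can therefore fall under 6.5.2, which ends study participation, and under 9.1.1, which ends only treatment. Two sites that each follow the protocol could handle that patient in opposite ways.

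A treatment-policy estimand counts events after the stop as well as before it, so it depends on continued device follow-up. A site that follows 6.5.2 delivers less data than 2.1 requires. The loss is tied to tolerability, and therefore to treatment. In an open-label comparison of two consecutive periods, it falls on whichever period the DLT occurred in.

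**Working it through.** **1. What is lost.** Protocol 8.5 has device reports exported at visits: baseline and Months 1, 3, 6, 9 and 12. Table 8-1 shows the same schedule.

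| Patient status after a DLT | Visits | Device data |
|---|---|---|
| Treatment stopped, attends as scheduled (8, 9.1.1) | Table 8-1 | to Month 12 |
| Treatment stopped, abbreviated contact (9.1.1) | clinic, telephone or e-mail | not in the minimum list |
| Withdrawn from the study (6.5.2; 8) | one final visit, if the patient agrees | to that visit at most |

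The final visit carries the final-visit assessments, and these include device data. Only the record after that visit is lost.

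**2. Whether the analysis repairs it.** Protocol 12.4.4 is complete-case, 12.4.5 has no sensitivity analysis, and SAP 7.2.1 imputes no outcome data. SAP 7.4.1 adds a 3-month comparison, which helps only if withdrawal comes after Month 9. Nothing restores the missing months.

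**3. The plan's sample size.** Inputs from Protocol 12.8.1: SVT in 8/120 (ACEI/ARB) and 1/120 (ARNI), two-sided 0.05, power 0.8, dropout 20%.

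- Discordant proportion: 8/120 × 119/120 + 1/120 × 112/120 = 0.0739.
- Difference: 8/120 × 119/120 − 1/120 × 112/120 = 0.0583.
- Exact sign test, averaged over the binomial number of discordant pairs: the smallest n with power of at least 0.80 is 175 (80.2%).
- 175/0.8 = 218.75, rounded up to 219, so 219 − 175 = 44 patients are allowed for dropout.

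The plan's figures reproduce. If DLT withdrawals are among the 44, power does not change. If they come on top, for assumed extra losses of:

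- 2%: 219 × 0.78, so 170 pairs, power 78.7%
- 5%: 219 × 0.75, so 164 pairs, power 76.8%
- 10%: 219 × 0.70, so 153 pairs, power 72.8%

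**4. Size of the distortion in the ARNI SVT proportion.** The documents give no DLT rate, so these inputs are assumptions: a share w of 5% or 10% of pairs whose ARNI window ends halfway, and a constant hazard. With six-month risk p, the half-window risk is h = 1 − (1 − p)^0.5. For p = 8/120, h = 3.39%; for p = 1/120, h = 0.42%.

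- Shortened window without an event counted as no event: p(1 − w) + wh.
- Such a window dropped: [p(1 − w) + wh] / [(1 − w) + wh].
- Treatment-policy value: p(1 − w) + w × (risk over the full six months, including the time off ARNI).

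Case A has no true difference (8/120 in both periods). Case B is the planned effect, with patients returning to the ACEI/ARB hazard after stopping ARNI. Their full-window risk is then 1 − (119/120)^0.5 × (112/120)^0.5 = 3.79%.

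| Case | w | Treatment-policy value | Counted as no event | Dropped if no event |
|---|---|---|---|---|
| A | 5% | 6.67% | 6.50% | 6.83% |
| A | 10% | 6.67% | 6.34% | 7.02% |
| B | 5% | 0.98% | 0.81% | 0.86% |
| B | 10% | 1.13% | 0.79% | 0.88% |

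The largest gap is 7.02 − 6.67 = 0.35 percentage points. Earlier withdrawal makes it larger: in case A with w = 10% and follow-up ending after one month of ARNI, counting as no event gives 6.00% + 0.1 × 1.14% = 6.11%, a gap of 0.55 points. With device data through Month 12, the recorded proportion equals the treatment-policy value in every row.

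**The case against.** The best defence is that very few patients may be affected. The trigger is a DLT defined in the product label, and the documents reproduce no such list. Protocol 6.2.3, 6.5, 6.5.1 and 6.5.3 deal with toxicity mainly by down-titration, interruption and re-initiation, and 9.1.1 leaves severe events to the investigator's discretion. A site might also simply let 9.1.1 govern. The final visit preserves device data up to the exit, and the 20% allowance exists to absorb withdrawals.

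All of this stands as an argument about size. It does not remove the contradiction. The rule in 6.5.2 is unconditional and the SAP repeats it. Neither document says that 9.1.1 takes precedence, and the data lost are those the stated estimand depends on.

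One could add that the fix recovers only part of the loss. That is also true. The SAP efficacy set requires at least one ARNI dose, so a patient with a DLT on ACEI/ARB is recovered only if ARNI is still started.

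**Conclusion.** The contradiction is real and certain from the text. Its consequence is minor to moderate and cannot be quantified from the documents. Under the stated assumptions, SVT moves by a few tenths of a percentage point. Power falls only if these losses exceed the dropout allowance.

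Four stronger readings are tempting, and the documents do not support them.

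- *The trial is underpowered because of this rule.* Nothing indicates that DLT withdrawals would come on top of the 44 already allowed for.
- *Reporting both codings of a shortened window would bracket the truth.* In case B both codings lie below the treatment-policy value (0.79% and 0.88% against 1.13% at 10% affected). The documents say nothing about risk after ARNI is stopped, so bracketing cannot be assumed. Dropping only event-free windows is also selective, because it keeps shortened windows with an event.
- *The coding gap is part of this fault.* Protocol 12.4.4 points towards treating such a window as an incomplete pair, while the SAP efficacy set admits patients who withdrew after one ARNI dose. That uncertainty concerns every early withdrawal and is a separate question.
- *The ablation rule in Protocol 6.2.1 is the same error.* It reads "if radiofrequency ablation is necessary, the patient should withdraw from the study". Ablation acts on the endpoint itself, so keeping later data out of the primary analysis is defensible. The only gap is that 2.1 names no strategy for ablation.

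**What to change.** 1. Reword Protocol 6.5.2 and SAP 3.3.2: a label-defined DLT stops study drug, and the patient remains in the study and attends the Table 8-1 visits unless consent is withdrawn.
2. Add device interrogation through Month 12 to the minimum data in Protocol 9.1.1. Without this, aligning 6.5.2 with 9.1.1 would still leave patients on abbreviated follow-up without endpoint data.

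The cost is wording in three sections, the amendment and ethics approval that Protocol 14.1 requires, and a few extra downloads from a device already implanted. Sample size, visit schedule and primary test do not change.
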